7. RESEARCH QUESTION AND OBJECTIVES

Primary Objective

To compare OS between patients with metastatic BRAFV600-mutant melanoma initiating encorafenib plus binimetinib (ENCO+BINI) versus dabrafenib plus trametinib (DAB+TRAM) or vemurafenib plus cobimetinib (VEM+COBI)

Exploratory Objective

To compare progression free survival (PFS) between patients with metastatic BRAFV600mutant melanoma initiating ENCO+BINI versus DAB+TRAM or VEM+COBI

This objective is designated as exploratory as, unlike for OS, differences in assessment of PFS between clinical trial data (CTD) and real-world data (RWD) settings may exist that preclude valid comparisons of this outcome across these settings. Suitability of comparative analyses of PFS will be determined following additional exploration to characterize number and frequency of assessments of PFS, and further analyses of comparability of PFS outcomes across trial and real-world settings.

8. RESEARCH METHODS

8.1. Study design

This is a retrospective cohort study comparing OS outcomes between patients with BRAFV600-mutant metastatic melanoma initiating ENCO+BINI versus DAB+TRAM or VEM+COBI. Comparisons will be adjusted for differences in baseline characteristics across treatment groups, and account for missing data on adjustment factors. PFS will also be investigated as an exploratory endpoint, subject to comparability of PFS outcome assessment between clinical trial and real-world settings.

8.2. Setting

Patients with BRAFV600-mutant metastatic melanoma initiating treatment with ENCO+BINI, DAB+TRAM or VEM+COBI.

8.2.1. Inclusion criteria

Inclusion criteria that will be used to identify patients initiating the targeted therapies of interest are provided separately for the clinical trial and real-world data sources below.

8.2.1.1. COLUMBUS trial

Key inclusion criteria in the COLUMBUS trial were:

- Histologically confirmed diagnosis of locally advanced, unresectable, or metastatic cutaneous melanoma or unknown primary melanoma
- American Joint Committee on Cancer (AJCC) disease stage of IIIB, IIIC, IVM1a, IVM1b, or IVM1c at trial enrolment
- Presence of BRAF V600E or V600K mutation in tumor tissue prior to enrollment
- At least 18 years of age at randomization
- Eastern Cooperative Oncology Group (ECOG) status of 0 or 1 at randomization
- Treatment naive or had progressed on or after previous first-line (1L) immunotherapy at randomization with no prior BRAF- or MEK-inhibitor therapy in the adjuvant setting

Patients from the COLUMBUS trial included in this analysis will be those patients:

Randomized to ENCO+BINI arm of the trial to receive 450mg once daily encorafenib
and 45mg twice daily binimetinib combination therapy

8.2.1.2. Flatiron Health data

Pfizer has contracted with Flatiron for a custom data extract containing information on patients with advanced melanoma. Eligibility criteria applied to the Flatiron custom data received by Pfizer include:

- Diagnosed with melanoma based on International Classification of Disease 9th and 10th Revisions (ICD-9: 172.x; ICD-10: C43x, D03x) and ≥2 visits on different days in the Flatiron database on or after January 1, 2011.
- Clinically confirmed diagnosis of melanoma with pathologic stages III or IV at initial diagnosis or earlier stage disease with a first locoregional or distant recurrence on or after January 1, 2011.
- Age ≥18 years at the time of advanced melanoma diagnosis.
- Evidence of ≥1 BRAF positive test result at any time based on laboratory or genetic analysis results.
- Treatment with ≥1 BRAF-inhibitor (i.e., encorafenib, dabrafenib, vemurafenib) and treatment with ≥1 MEK-inhibitor (i.e., binimetinib, trametinib, cobimetinib) in 1L or 2L line of therapy (LOT), as defined per Flatiron's LOT business rules.

 Earliest LOT containing a BRAF- and MEK-inhibitor ≥3 months prior to data cutoff (defined as 30 September 2021)

Key inclusion criteria from the COLUMBUS trial will be applied to the Flatiron RWD population to align the populations to the extent possible between the CTD and RWD sources. The sample of patients from the Flatiron Health EHR data for this study will be identified using the following additional criteria applied to the custom data cut received from Flatiron:

- At least 18 years of age at the index date
- Confirmed BRAF V600E or V600K activating mutation reported in the data based on laboratory or genetic analysis results
- Treatment-naive or had previous 1L IO at index date in the therapeutic setting, based on review of medication orders or administration prior to the index date.
- ECOG status of 0 or 1 at the index date

The following criteria will be additionally used to identify patients receiving each of the treatments of interest:

- ENCO+BINI treatment group: At least 1 order or administration of ENCO+BINI treatment after the diagnosis of metastatic melanoma and after 27 June 2018 (FDA approval date for ENCO+BINI for use in patients with metastatic melanoma).
- DAB+TRAM treatment group: At least 1 order or administration of DAB+TRAM treatment after the diagnosis of metastatic melanoma and after 09 January 2014 (FDA approval date for DAB+TRAM for use in patients with metastatic melanoma).
- VEM+COBI treatment group: At least 1 order or administration of VEM+COBI treatment after the diagnosis of metastatic melanoma and after 10 November 2015 (FDA approval date for VEM+COBI for use in patients with metastatic melanoma).

The index date in each treatment group will be the date of treatment initiation.

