8.3. Variables

Table 1 provides a summary of exposure, outcome, and patient baseline characteristics that will be evaluated within the study.

Table 1. Key exposures, outcomes, and patient baseline characteristics

Variable	Role	Data source(s)	Operational definition/categories
Treatment group (ENCO+BINI, DAB+TRAM, VEM+COBI)	Exposure	COLUMBUS trial data; Flatiron EHR	Indicates whether patients initiated ENCO+BINI, DAB+TRAM or VEM+COBI treatment
os	Primary Outcome	COLUMBUS trial data, Flatiron	In the COLUMBUS trial data, defined as the time from the date of randomization to the date of death due to any cause; if death is not observed, patients will be censored at the date of last contact or the data analysis cut-off date (e.g., 15 September 2020), whichever occurs first
	Timaly outcome		In Flatiron EHR, will be defined as the time from the index date to the date of death; patients without a date of death will be censored at their last known activity date (e.g., the last clinical note date) or the end of the follow-up period, whichever occurs first
	COLUMBUS	In the COLUMBUS trial data, defined as the time from the date of randomization to the date of the first documented disease progression or death due to any cause, whichever occurred first; if a patient did not have an event at the analysis cut-off date, PFS will be censored at the date of the last adequate tumour assessment	
PFS	Exploratory Outcome	trial data, Flatiron her	In Flatiron EHR, will be defined as the time from the index date to either the date of first disease progression event or death in the absence of progression; patients without disease progression or death will be censored at the last date the patient could have been assessed for progression (e.g., the last clinical note date) or the data analysis cut-off date (e.g., 30 September 2021), whichever occurs first
Age at baseline (years)	Baseline Characteristic / Potential Confounder	COLUMBUS trial data Flatiron EHR	Patient age; defined at the time of study randomization for COLUMBUS trial data and at the time of treatment initiation for Flatiron EHR
Sex	Baseline Characteristic / Potential Confounder	COLUMBUS trial data; Flatiron EHR	Male, Female, Intersex, or Unknown/Missing

Race	Baseline Characteristic / Potential Confounder	COLUMBUS trial data; Flatiron EHR	Asian, Black, White, Other/Multi-Race, or Unknown/Missing

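### The Flatiron two-visit rule is not tied to the index date, so a patient whose second visit follows treatment start has guaranteed survival to that visit; COLUMBUS patients face no such condition

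*Protocol*

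**What the plan says.** Protocol 8.2.1.2 and SAP 4.1 describe the Flatiron extract in the same words. One entry condition is at least two "visits on different days in the Flatiron database on or after January 1, 2011". It has a start date but no end date, and it does not refer to treatment.

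The time origin is set separately: "The index date in each treatment group will be the date of treatment initiation". For the outcome, Protocol 8.3 (Table 1) states: "In Flatiron EHR, will be defined as the time from the index date to the date of death", and SAP 5.1 (Table 2) agrees. Neither document mentions delayed entry, left truncation, a landmark, or a minimum period of Flatiron activity before index.

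Cohort membership needs one treatment record, for example "At least 1 order or administration of DAB+TRAM treatment after the diagnosis of metastatic melanoma and after 09 January 2014" or "At least 1 order or administration of ENCO+BINI treatment after the diagnosis of metastatic melanoma and after 27 June 2018". That record is not required to be the first dose. Treatment-naive or prior-immunotherapy status is judged "based on review of medication orders or administration prior to the index date", with no minimum look-back.

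COLUMBUS patients (n=192 in the ENCO+BINI arm, Protocol 8.4) are followed from randomization and are not subject to the visit rule. The limitations in Protocol 8.9 and the sensitivity analyses in SAP 7.1 do not raise the point.

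**The concern.** Because visits after treatment start count towards eligibility, inclusion can depend on the future. Take a patient with fewer than two Flatiron visits by index. If that patient dies before the second visit, the extract never contains them. If they survive to it, they are included and credited with the whole interval from index, in which death was impossible by construction.

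The visit filter falls unevenly on the two sides of the primary contrast. DAB+TRAM and VEM+COBI come entirely from Flatiron. ENCO+BINI pools a Flatiron cohort, which passes the same filter, with COLUMBUS patients, who do not. The contrast is therefore Flatiron against COLUMBUS, diluted within the pooled arm. Any effect works against ENCO+BINI. Adjusting for baseline covariates cannot remove a condition on survival after baseline.

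**Working it through.** The documents give no figure for visit timing, no planned sample size and no event count, so there is nothing to reproduce. The check has two parts.

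**1. Does another rule close the gap?**
- *Treatment record:* it must follow the metastatic diagnosis and the approval date, but it need not coincide with index.
- *ECOG 0 or 1 at index:* read strictly, this implies contact near index. However, Table 1 allows ECOG to be unknown or missing, and Protocol 8.7.3 imputes it.
- *Three-month baseline window (8.7.1):* it says where covariates come from and does not require a visit.
- *Treatment start at least 3 months before the 30 September 2021 cutoff:* it limits calendar time and does not require observation at index.

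None of these rules ensures two visits by index.

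**2. How large could the effect be?**

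Assumptions, none from the documents: true HR 1; exponential OS with median 20 months; censoring at 60 months; equal groups; COLUMBUS a share c = 65% to 100% of the ENCO+BINI arm. With 192 COLUMBUS patients, c = 65% means 192/0.65 ≈ 295 in the arm, so about 103 from Flatiron. A share q of Flatiron patients, before selection, have their second visit at time D after index. D is exponential with mean m, independent of survival time T, and these patients are kept only if T > D.

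- Hazard: λ = ln 2/20 = 0.0347 per month; μ = 1/m; S(t) = exp(−λt).
- Chance of being kept: P = μ/(μ+λ).
- Survival of those kept: S_sel(t) = [exp(−λt) − (λ/(λ+μ))·exp(−(λ+μ)t)]/P.
- Their share of the retained cohort: w = qP/(1 − q + qP).
- Flatiron curve: S_F = (1−w)S + w·S_sel. ENCO+BINI curve: S_E = cS + (1−c)S_F.
- Large-sample Cox HR: the exp(β) that solves the score equation for S_E against S_F over 0–60 months.

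For q = 20% and m = 12: P = 0.0833/0.1180 = 0.706; share removed = 0.20 × 0.294 = 5.9%; w = 0.141/0.941 = 0.150.

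| q, m | P | Removed, q(1−P) | HR, c = 65% | HR, c = 100% |
|---|---|---|---|---|
| 25%, 1 month | 0.967 | 0.8% | 1.006 | 1.009 |
| 10%, 6 months | 0.828 | 1.7% | 1.011 | 1.017 |
| 20%, 12 months | 0.706 | 5.9% | 1.033 | 1.051 |

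If 20% and 12 months describe the retained patients instead, their survival is the sum of an exponential gap with mean 12 months and a further exponential time with hazard λ. The HR is then 1.06 to 1.10.

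A separate calculation used a fixed gap and a wholly unselected ENCO+BINI arm. For 25% of patients and 1 month, it gives a comparator HR of 0.986 to 0.991 over medians of 12 to 24 months. The reciprocals are 1.014 to 1.009, in line with the first row.

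With delayed entry, the late entrants at risk at time t are those with D ≤ t < T. When D is independent of T their hazard is λ, so the HR returns to 1.

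**The case against.** The strongest reply is that the affected group may be small or empty. Visits count from 2011, while eligible index dates start only after January 2014, November 2015 or June 2018. Diagnosis and prescribing would ordinarily bring patients to the clinic before treatment starts. The ECOG criterion also points to contact near index. All of this stands as a limit on size. It does not remove the gap, because nothing in the plan would show whether the share is negligible or substantial.

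A reader might infer more: that comparators do carry guaranteed survival time, that patients who began treatment outside the network are kept with their outside start date, and that undetected earlier BRAF or MEK inhibitor treatment is present. The documents do not support these statements.
- They do not show that any patient has fewer than two visits by index.
- They do not say that an out-of-network start date is captured. If index is the first in-network record, gaps of 6 to 12 months would not arise from late joining.
- The review of orders is stated for the treatment-naive and prior-immunotherapy criterion. The exclusion for earlier BRAF or MEK inhibitors names no method, and the database includes physician notes (Protocol 8.4).
- The two mechanisms partly conflict: long guaranteed time through late joining needs outside treatment dates to be recorded, while missed prior treatment needs outside treatment to go unrecorded.

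**Conclusion.** The point holds as a gap in the cohort definition, with a probably small effect of known direction. Any Flatiron patient whose second visit follows index has guaranteed survival to that visit. COLUMBUS patients have none, so the pooled comparison does not fully cancel it. Under the assumptions above, the ENCO+BINI HR moves from 1 to about 1.01 in the mild case and 1.03–1.05 in the 20%, 12-month case. The range 1.06–1.10 needs those values to hold among retained patients. Appendix Table 3 uses ENCO+BINI as the reference, so there the effect would appear as the reciprocal: 1/1.03 = 0.97 to 1/1.05 = 0.95.

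The shares and gaps are illustrative, since the documents give none. Missed prior therapy in patients with no Flatiron record before index is possible but not shown, and no size is claimed for it here. An improvement is still worth making because it is nearly free and the plan as written cannot reveal the share.

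**What to change.** 1. In Protocol 8.7.2 and 8.7.4 and SAP 7.1, state that in the Kaplan-Meier and Cox analyses of OS each Flatiron patient enters the risk set at the later of the index date and the second-visit date. COLUMBUS patients enter at randomization. Time is still measured from index or randomization.
2. Report, by treatment group and data source, the number of patients without two visits, and the number without any visit, on or before index.
3. As a sensitivity analysis, repeat the primary model keeping only those Flatiron patients with at least one visit before the index date. A visit on the index date should not qualify: it would satisfy the three-month window but show nothing about earlier treatment.

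Two visits by index should not be made an eligibility rule, because that would drop patients treated from their first visit.

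The cost is a few sentences and an entry-time argument in the code; Protocol 8.4 lists visits among the structured data. Delayed entry keeps everyone in the cohort but makes early risk sets slightly smaller, and a patient censored on the second-visit date adds no time at risk. It also assumes that the timing of the second visit is unrelated to prognosis, which the SAP should state. The restricted repeat does lose patients, which is why it belongs among the sensitivity analyses.

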₹ Pfizer C	CLINICAL AND MEDICAL CONTROLLED DOCUMENT (CMCD) REQUIRED FORM/TEMPLATE			
Identifier	Version	Title	Effective Date	
CT24-WI-GL02-	2.0	SUMMARY OF CHANGES IN	01-Jun-2022	
RF07		AMENDED NON-INTERVENTIONAL		
		STUDY PROTOCOL		

Protocol #: C4221028

OCEANMIST - Comparative effectiveness of different targeted therapies for BRAF-mutated unresectable/metastatic melanoma in the United States

SUMMARY OF CHANGES IN AMENDED NON-INTERVENTIONAL STUDY PROTOCOL

This amended protocol describes a revised approach for assessment of comparative effectiveness of encorafenib plus binimetinib relative to other targeted therapies for BRAF-mutated unresectable/metastatic melanoma. Analyses conducted based on the originally submitted protocol for study C4221028 were limited to descriptive and unadjusted analyses of real-world data from Flatiron Health, as the sample size of the identified encorafenib plus binimetinib study cohort was judged to be too small for conduct of adjusted comparative effectiveness analyses. Based on the findings of a recently completed study (*Protocol #C4221035: Overall survival (OS) in patients with metastatic BRAFV600-mutant melanoma treated with encorafenib plus binimetinib in the COLUMBUS trial versus in real-world practice data)*, which showed consistent OS outcomes between the COLUMBUS trial Flatiron Health after accounting for differences in patient profiles, in this amended protocol, to enrich the sample size for the encorafenib plus binimetinib combination cohort, data will be pooled across Flatiron and COLUMBUS, and compared versus real-world data for other targeted therapies as described further below.

Key elements of the revised approach are summarized below:

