8.4. Data sources

COLUMBUS trial

COLUMBUS was a two-part, multicenter, randomized, open-label, Phase 3 clinical trial. ¹⁰ Part 1 of the trial investigated the effectiveness and safety of three treatment regimens in patients with locally advanced unresectable or metastatic BRAFV600-mutant metastatic melanoma who were treatment naïve or whose cancer had progressed after 1L IO. In Part 1 of the trial, patients were randomized to one of three treatment arms: 1) 450mg once daily encorafenib and 45mg twice daily binimetinib (n=192), 2) 960mg twice daily vemurafenib (n=191) and 3) 300mg once daily

encorafenib (n=194). Randomization was stratified by AJCC disease stage (IIIB, IIIC, IVM1a, IVM1b, or IVM1c), ECOG performance status (0, 1), and BRAFV600 mutation profile (V600E, V600K). Progression-free survival was the primary endpoint in the trial, while OS was one of the secondary endpoints. Patients were enrolled in Part 1 of the trial between 30 December 2013 through 10 April 2015.

The ENCO+BINI arm of Part 1 of the trial will be used in this study (database lock date: 15 September 2020). Part 2 of the trial compared encorafenib 300mg once daily plus binimetinib 45mg twice daily versus encorafenib 300mg once daily alone and will not be considered.

Flatiron Health EHR

The Flatiron Health EHR database is a longitudinal, de-identified real-world database derived from EHRs collected in US cancer clinics. The database covers more than 2.6 million active cancer patients treated at over 800 sites of care across 4 US census regions. Patient-level data includes both structured (diagnosis, demographics, laboratory values, biomarker information, drug orders, visits, etc.) and unstructured (physician notes, radiology, and pathology reports, etc.) sources. Data on death is drawn from structured or unstructured data fields in the EHR, and publicly available sources of mortality including the US Social Security Death Index, and commercial obituary data. ¹³

Pfizer has contracted with Flatiron for a custom data extract containing information on patients with advanced melanoma who received treatment with BRAF- or MEK-inhibitor therapies. Patients meeting the eligibility criteria defined for this study will be obtained from this custom data extract as described in Section 8.2 and used in all analyses.

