2.1 STUDY DESIGN

This is a retrospective cohort study comparing OS outcomes between patients with BRAFV600-mutant metastatic melanoma initiating encorafenib plus binimetinib (ENCO+BINI) versus dabrafenib plus trametinib (DAB+TRAM) or vemurafenib plus cobimetinib (VEM+COBI). Comparisons will be adjusted for differences in baseline characteristics across treatment groups, and account for missing data on adjustment factors. PFS will also be investigated as an exploratory endpoint, subject to comparability of PFS outcome assessment between clinical trial and real-world settings.

Study population

The study population will consist of patients with BRAFV600-mutant metastatic melanoma initiating treatment with ENCO+BINI, DAB+TRAM or VEM+COBI. Data for ENCO+BINI will be pooled across COLUMBUS and Flatiron data, while data for DAB+TRAM and VEM+COBI will be from Flatiron data. The number of patients eligible for the study will be determined in accordance with the sample selection conducted per the inclusion and exclusion criteria described in Section 4.

Data source

COLUMBUS trial

COLUMBUS was a two-part, multicenter, randomized, open-label, Phase 3 clinical trial. Part 1 of the trial investigated the effectiveness and safety of three treatment regimens in patients with locally advanced unresectable or metastatic BRAFV600-mutant metastatic melanoma who were treatment naïve or whose cancer had progressed after 1L IO. In Part 1 of the trial, patients were randomized to one of three treatment arms: 1) 450mg once daily encorafenib and 45mg twice daily binimetinib (n=192), 2) 960mg twice daily vemurafenib (n=191) and 3) 300mg once daily encorafenib (n=194). Randomization was stratified by AJCC disease stage (IIIB, IIIC, IVM1a, IVM1b, or IVM1c), ECOG performance status (0, 1), and BRAFV600 mutation profile (V600E, V600K). Progression-free survival was the primary endpoint in the trial, while OS was one of the secondary endpoints. Patients were enrolled in Part 1 of the trial between 30 December 2013 through 10 April 2015.

The ENCO+BINI arm of Part 1 of the trial will be used in this study (database lock date: 15 September 2020) and combined with the ENCO+BINI cohort from Flatiron EHR identified below. Part 2 of the trial compared encorafenib 300mg once daily plus binimetinib 45mg twice daily versus encorafenib 300mg once daily alone and will not be considered.

Flatiron Health EHR

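### The Flatiron criteria set no date limit on the qualifying BRAF V600E/K result, so any patient who qualifies only on testing after treatment start contributes guaranteed survival time, mainly in the comparator groups

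*Protocol*

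**What the plan says.** Two Flatiron criteria concern BRAF, and neither carries a date limit. The extract-level one asks for "Evidence of ≥1 BRAF positive test result at any time based on laboratory or genetic analysis results" and covers any BRAF-positive result. The study-level one asks for "Confirmed BRAF V600E or V600K activating mutation reported in the data based on laboratory or genetic analysis results". SAP 4.1 repeats both.

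For the trial patients, Protocol 8.2.1.1 states "Presence of BRAF V600E or V600K mutation in tumor tissue prior to enrollment".

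The other Flatiron conditions that this study adds on patient status are anchored in time. Age, prior treatment and ECOG refer to the index date (8.2.1.2), and central nervous system metastases count only if they precede index (8.2.2).

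On time zero, 8.2.1.2 says "The index date in each treatment group will be the date of treatment initiation". Table 1 in 8.3 gives OS: "In Flatiron EHR, will be defined as the time from the index date to the date of death". No delayed entry is described. On sources, SAP 2.1 says "Data for ENCO+BINI will be pooled across COLUMBUS and Flatiron data, while data for DAB+TRAM and VEM+COBI will be from Flatiron data".

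**The concern.** Eligibility that can be met by an event after time zero selects on survival. Consider two hypothetical Flatiron patients who start the same regimen with only an unspecified BRAF-positive result on file. One lives long enough to be re-tested and is found to carry V600E; the other dies before any re-test. Read literally, the criteria admit the first, with all follow-up from treatment start, and exclude the second.

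The time before the qualifying test is then person-time in which death was impossible. It lowers the apparent death rate wherever it occurs. COLUMBUS patients cannot contribute any, so it falls in both comparators and only in the Flatiron part of ENCO+BINI. The primary hazard ratio (ENCO+BINI versus comparator) would be pushed above its true value. Neither the Cox covariates nor the imputation of baseline data can remove it, because the distortion lies in who enters and when.

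**Working it through.** **Does any passage close the window?** I found none. The limitations in Protocol 8.9 do not mention test timing. The optional sensitivity analyses in SAP 7.1 cover extra covariates and period of treatment initiation. The baseline table shell has no row for test date.

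**Inputs from the documents.** COLUMBUS contributes 192 ENCO+BINI patients (Protocol 8.4). The Flatiron ENCO+BINI cohort has no stated size; in the earlier analysis it "was judged to be too small for conduct of adjusted comparative effectiveness analyses" (Protocol, Summary of Changes). No event count, median OS or late-tested share is given, so there is no plan figure to reproduce.

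**Assumptions.** True HR 1.00; exponential OS with median 12 or 24 months; censoring at 36 or 60 months; a share f of included Flatiron patients qualifying only on a test at a mean of d months after index (uniform from 0 to 2d); a share w of ENCO+BINI from Flatiron. For scale, 48 Flatiron patients would give w = 48/(192+48) = 0.20, and 95 would give 95/(192+95) = 0.33.

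**Hand check of one case** (median 12, censoring 36, d = 6, f = 20%, w = 0).
- Death rate λ = ln 2/12 = 0.0578 per month.
- Mean follow-up without guaranteed time: (1 − e^(−36λ))/λ = (1 − 0.125)/0.0578 = 15.15 months.
- Mean at-risk time after the test for a late-tested patient: (1 − 0.125 × 1.4427)/0.0578 = 14.19 months, where 1.4427 is the mean of e^(λ·delay) over 0–12 months, (2 − 1)/ln 2.
- At-risk time per comparator patient: 0.8 × 15.15 + 0.2 × 14.19 = 14.96 months. Guaranteed time: 0.2 × 6 = 1.2 months.
- Apparent HR ≈ (14.96 + 1.2)/14.96 = 1.08.

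The simulated Cox estimate for this case is 1.086, so the two methods agree closely.

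**Simulated HR, ENCO+BINI versus comparator** (400,000 per arm, Monte Carlo error about 0.003), with d = 6 and w = 0:

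| Median OS / censoring (months) | f = 2% | f = 5% | f = 10% | f = 20% |
|---|---|---|---|---|
| 12 / 36 | 1.007 | 1.020 | 1.037 | 1.086 |
| 12 / 60 | 1.006 | 1.021 | 1.037 | 1.069 |
| 24 / 36 | 1.008 | 1.015 | 1.025 | 1.058 |
| 24 / 60 | 1.003 | 1.013 | 1.023 | 1.043 |

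Shorter delays shrink the effect: with d = 1 and f = 20% the range is 1.002–1.015. A larger Flatiron share of ENCO+BINI also shrinks it. The 1.086 becomes 1.065 at w = 0.20 and 1.051 at w = 0.33.

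**Other assumptions.** With 24-month median OS, w = 0.25 and uniform censoring over 3–60 months, a mean guaranteed interval of 5 or 9 months gives 1.02 or 1.04 at f = 10%, and 1.04 or 1.07 at f = 20%. Shares of 1–2% give 1.003–1.008. Follow-up windows built from the documents' own dates give 1.02–1.03 at 10% and 1.03–1.06 at 20%.

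Appendix Table 3 uses ENCO+BINI as the reference, so there the effect would appear as the reciprocal: 1.04 becomes 1/1.04 = 0.96.

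**The case against.** The strongest reply is that the affected group may be almost empty. Every patient started a BRAF/MEK inhibitor pair, and Protocol 6 ties the ENCO+BINI indication to a mutation detected by an approved test. Testing before treatment is therefore the expected order, although for the comparators this is inference. Re-testing a patient already known to carry V600E/K does no harm; only a first qualifying result from later testing matters. This stands, and it is why the size is called probably small.

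A reader might infer that the plan expressly accepts V600E/K results obtained after treatment start. It does not. The any-time wording belongs to the extract condition on any BRAF-positive result, and the V600E/K criterion simply gives no date. Protocol 8.9 also lists the BRAF criterion among those aligned with COLUMBUS to the extent possible. That supports calling this an unstated limit, but it does not supply the limit.

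A reader might also infer that DAB+TRAM must be hit hardest. From approval to the 30 September 2021 cutoff, the longest possible window is about 93 months for DAB+TRAM, 71 for VEM+COBI and 39 for Flatiron ENCO+BINI. A longer window permits more late testing, but the documents give no testing frequency, so a difference between Flatiron groups is only possible.

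Finally, a result reported after index on a specimen already sent for testing before index does not require survival. A rule based on report date alone would drop valid patients. This is correct, and the fix allows for it.

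**Conclusion.** The gap in the criteria is real, and the mechanism follows from the plan's own definitions. Its size is unknown and probably modest: an apparent HR of about 1.00–1.04 when the truth is 1.00 and 1–10% of Flatiron patients are late-tested, and up to about 1.09 at 20%. The upper figure assumes a six-month mean delay, 12-month median OS, censoring at 36 months and a negligible Flatiron share in ENCO+BINI; longer delays would raise it. All shares and delays are assumptions.

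The documents do not support reading this as evidence that the comparison is materially distorted. Nor can this mechanism by itself create an apparent ENCO+BINI advantage, since it works in the opposite direction. It should be corrected because it is systematic, no planned analysis would reveal it, and the remedy is cheap.

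**What to change.** In Protocol 8.2.1.2 and SAP 4.1:

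- Require the qualifying V600E/K evidence to come from a specimen collected on or before the index date. Use the result date where the specimen date is unavailable, and state a rule for undated results. Apply this to all three Flatiron cohorts.
- Report, per treatment group, how many patients qualify only on later testing. Count separately those with a pre-index specimen but a post-index result, because archived tissue first sent for testing after index would still imply survival to that point.
- As a sensitivity analysis, include the later-tested patients with delayed entry at the test date in the Kaplan-Meier and Cox analyses.

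Under the working's assumptions, excluding these patients or entering them at the test date removes the guaranteed time and returns the HR to 1.00. The cost is one date condition, one reported count and one extra model run. The downside is a loss of Flatiron patients, probably small, which the count will show. Protocol 5 planned completion of analyses for June 2023; if they have already been run, the count and one rerun would settle whether this matters.
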